7.3 Analysis of the Primary Efficacy Endpoint

The primary study endpoint is the proportion of Achilles infusion sets that function each day of use, up to 7 days. This endpoint will serve as both the preliminary effectiveness and safety endpoint during the feasibility evaluation.

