1.4 Study Synopsis

1.4.1 Overview

This is a prospective, non-randomized, home-use feasibility study of device performance, usability, tolerability, and safety of an investigational infusion set for continuous subcutaneous

insulin infusion (CSII or insulin pump therapy) in up to 20 participants diagnosed with type 1 diabetes mellitus (T1DM). The Capillary Biomedical, Inc. (CapBio) Achilles infusion set is a sterile single use device designed to be used with commercially available infusion pumps (e.g., Medtronic MiniMed). The investigational Achilles infusion set contains a coil reinforced soft polymer indwelling cannula with one distal and three proximal holes (see item 2 Investigational Device).

The existing patient population at the study center will be screened for study eligibility within 21 days of planned study enrollment. Eligible participants will complete written informed consent and be assigned a study identifier.

The study is comprised of 3 periods. Each period is initiated at the study center and followed by a home-use phase of up to 7 days (Figure 1):

1. Week 1 (t = 7 days): Trial run with saline infusion. Patients will continue to use their own pump and insulin infusion set while wearing the CapBio Achilles infusion set connected to a second pump. The reservoir in this pump will be filled with saline and patients will mimic their insulin basal/bolus pattern on the dummy pump.
2. Week 2 (t ≤ 7 days): After successful completion of *Week 1*, patients will manage their blood glucose (BG) solely with their insulin pump and the Achilles infusion set. BG will be closely monitored with a continuous glucose monitoring (CGM) device. *Week 2* is considered complete when either, (1) an Achilles infusion set failure (see below) occurs and participant needs to insert a commercial CSII set to maintain routine therapy until they return to the study center, or (2) participant has worn Achilles for the total 7-day wear period.

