After insertion of the Achilles infusion set at the study site, participants will be required to manage routine basal/bolus insulin therapy using study specific supplies only with their current insulin pump during two extended wear home use periods of up to 7 days each (*Week 2* and *Week 3*, respectively). Participants will monitor BG levels with Dexcom G5 CGM device to avoid glycemic excursions. Participants will conduct daily visual inspection and record Achilles insertion set location pain levels and skin reactions. If subject experiences an Achilles infusion set device issue, participants shall insert a commercial CSII set to maintain routine insulin therapy. Participants will be provided with training and written instructions if an Achilles device issue occurs at any time during home wear periods. They are instructed to contact study staff as early as possible after infusion set failure. *Week 2* evaluation period is complete when either, 1) an Achilles infusion set failure occurs and subject needs to insert a commercial CSII set to maintain routine therapy until they return to the study center, or 2) subject has worn Achilles for the total 7-day wear period.

Upon completion of *Week 2* wear period (either after full 7 days or earlier), participants are asked to return to study center. Data will be downloaded from the subject's insulin pump, ketone monitors and CGM. Patient Diaries will be collected after each wear period. All study supplies will be replenished as needed.

Week 3 evaluation begins when study center inserts another Achilles infusion set (Day 0c). Participants will maintain insulin pump therapy per standard of care. *Week 3* home use evaluation is considered complete when, 1) an Achilles device issue requires subject to insert a commercial CSII set; or 2) subject has worn Achilles for a second total 7 -day wear period.

Participants who do not participate in *Week 3* will exit the study at time of declination. All data up the point of study exit will be documented and included for analysis. Participants may exit the study at any time without prejudice to their ongoing medical care. The time and reason for early exit will be recorded, and all data up to the point of study exit shall be documented and included for analysis.

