5.4 Intended Performance/Success Criteria

Results of this study will be compared to those of Patel et al. (3), who observed that 30% of infusion sets performed adequately (no premature failure due to mechanical malfunction and no episodes of uncorrectable hyperglycemia prior to the end of 7 days of infusion set wear time), and, among infusion sets that did not exhibit mechanical malfunction, 60% performed adequately by the glucose control metrics for the 7-day wear period. Success criteria will be considered met if the Achilles infusion set exceeds these performance outcomes.

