7.1 General Approach

As a routine evaluation of the data during analysis, consistency of the study variables to properties of statistical tests will be checked. Descriptive statistics shall be used for independent variables.

For tabulated continuous variables, descriptive analyses will present the mean, standard deviation, median, minimum and maximum. For tabulated categorical variables, the number with the characteristic, the total number evaluated and the percent will be provided.

Unless otherwise specified, statistical analyses will be performed using vendor specified software products.

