7.2 Populations for Analysis

Intent-to-Treat (ITT) Analysis Population: All participants who meet all eligibility criteria and have undergone a first attempt to insert an investigational Achilles infusion set shall be included in the ITT analysis population.

Safety Analysis Population: All participants who had an investigational cannula inserted.

Per-Protocol (PP) Analysis Population: All patients who completed any part of the 7-day Achilles infusion set evaluation period.

The primary effectiveness analysis will be based on the ITT subject population. Sensitivity analyses of the primary effectiveness endpoint will be generated based on the PP population. The ITT population may contain some patients who did not complete the evaluation interval. This will require the use of imputation methods for missing values. Last observation carry forward will be used in such case.

The primary safety analysis will be based on the safety population. All secondary and exploratory effectiveness analyses will use both the ITT and PP populations.

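### Section 7.3 does not fix the denominator of the daily primary proportion or say how failed sets count on later days, so its Day-7 value may not be comparable with the cumulative 30% benchmark in 5.4

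*Combined protocol and SAP*

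**What the plan says.** The primary analysis in 7.3 rests on one sentence defining the quantity: "The primary study endpoint is the proportion of Achilles infusion sets that function each day of use, up to 7 days". It names no denominator and no estimator.

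Other sections bear on how to read it:

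- **End of a wear period.** In 1.4.1, Week 2 "is considered complete when either, (1) an Achilles infusion set failure (see below) occurs" or when the full 7 days have been worn. Section 2.9 repeats this, ending the period when "an Achilles infusion set failure occurs and subject needs to insert a commercial CSII set to maintain routine therapy". Week 3 follows the same pattern.
- **Percentages.** For categorical variables, 7.1 says "the number with the characteristic, the total number evaluated and the percent will be provided".
- **Missing data.** Section 7.2 bases the primary analysis on the ITT population and notes: "The ITT population may contain some patients who did not complete the evaluation interval". For these patients it prescribes last observation carried forward (LOCF).
- **Benchmark.** Section 5.4 cites an outside study that "observed that 30% of infusion sets performed adequately (no premature failure due to mechanical malfunction and no episodes of uncorrectable hyperglycemia". The same sentence sets the time frame, so that the 30% covers the whole 7-day wear period. The success rule follows: "Success criteria will be considered met if the Achilles infusion set exceeds these performance outcomes".

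**The concern.** Once a set fails, a commercial set replaces it, so the failed set has no later day of use. Its week is then complete by definition, so it is unclear whether the LOCF rule, which is meant for incomplete intervals, reaches it. Reporting over the number evaluated permits a denominator that shrinks each day. On that reading the daily figure is a conditional one-day success rate among surviving sets.

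The 30% in 5.4 is a different quantity: the share of all sets that last to the end of 7 days. If a conditional Day-7 rate were set against it, a device no better than the benchmark would appear to exceed it by a wide margin. At stake are the reported primary result and the success rule in 5.4.

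LOCF raises a second question. If a set is withdrawn while still working, carrying its last status forward counts it as a Day-7 success that was never observed.

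**Working it through.** The protocol contains no sample-size or power calculation to reproduce. The 30% is quoted from an outside study.

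**Inputs**
- Benchmark S(7) = 0.30 (5.4).
- At most 20 × 2 = 40 insulin sets (6.2.6; Weeks 2 and 3). This is a ceiling: 1.4.1 says up to 20 participants, and Week 3 is conditional.
- Table 1 (4.7), failure by day of use for existing sets: Day 1 >15%, Day 3 >25%, Day 7 >65%.
- The daily failure pattern of a benchmark-level device is not given. It is an assumption, varied below.

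**Step 1: constant hazard**
- Daily conditional function q = 0.30^(1/7) = 0.842.
- Sets entering Day 7: 40 × q^6 = 14.25. Functioning through Day 7: 40 × q^7 = 12.0.
- At-risk Day-7 proportion: 12.0/14.25 = 84.2%.
- All-sets Day-7 proportion: 12/40 = 30.0%.

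| Day | 1 | 2 | 3 | 4 | 5 | 6 | 7 |
|---|---|---|---|---|---|---|---|
| Over sets in use, % | 84.2 | 84.2 | 84.2 | 84.2 | 84.2 | 84.2 | 84.2 |
| Over all sets, % | 84.2 | 70.9 | 59.7 | 50.3 | 42.3 | 35.6 | 30.0 |

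**Step 2: other hazard shapes, S(7) held at 0.30**
- Weibull, S(t) = exp(-λt^k) with λ = -ln(0.30)/7^k. The at-risk value is S(7)/S(6) = exp(-λ(7^k - 6^k)). For k = 0.5, 1, 1.5, 2, 3 it is 91%, 84%, 78%, 73%, 64%.
- Linear decline, 0.10 lost per day: 0.30/0.40 = 75%.
- Logical limits: 30% if every failure falls on Day 7, 100% if none does.

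**Step 3: anchored on Table 1, S(3) = 0.75**
- Constant hazard over Days 4-7: (0.30/0.75)^(1/4) = 80% for S(7) = 0.30; (0.35/0.75)^(1/4) = 83% for S(7) = 0.35.
- Linear decline over Days 4-7: 0.30/(0.30 + 0.1125) = 73%; 0.35/(0.35 + 0.10) = 78%.
- Table 1 gives inequalities, so 0.75 and 0.35 are upper limits on function.

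**Step 4: LOCF for sets withdrawn while functioning**

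Let w of 40 sets be withdrawn while working, with 30% of the rest reaching Day 7. The reported value is (0.30 × (40 - w) + w)/40.
- w = 2: (11.4 + 2)/40 = 33.5%.
- w = 4: (10.8 + 4)/40 = 37.0%.

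**The case against.** The strongest reply is that the plan already leans towards the cumulative reading. The unit in 7.3 is the infusion set, with no restriction to sets still in use. Table 1 is laid out by days of use and its failure percentages rise, which fits cumulative reporting. Section 5.4 defines its own metric over the full 7 days and nowhere says that a conditional daily rate is compared with it. LOCF within ITT, applied to a failed set, would carry the failure forward and keep the denominator fixed. Finally, 5.3 disclaims a statistical hypothesis, and the failure counts in 6.1.4 and listings in 7.7 should let the cumulative figure be recovered.

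Much of this stands. A reader might infer that the plan's endpoint is the at-risk rate and that the trial will report about 84% for a benchmark-level device. The documents do not support that: cumulative and every-day readings are at least as open, and 84% needs a constant hazard. A reader might also infer that a worsening device could show a flat daily series. That is unsupported, because a rising pooled hazard lowers the conditional series, as the Weibull shapes above 1 show.

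The reply does not settle the choice, however. No section states the denominator, and because a week ending in failure is complete, the reach of LOCF is uncertain. A feasibility study that sets a numerical success rule still needs its primary proportion on the scale of that rule.

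**Conclusion.** The concern holds as an ambiguity. Section 7.3 leaves open both the denominator and the later-day status of failed sets. The same data from a device at the benchmark could be reported on Day 7 as 30% (cumulative) or, on the at-risk reading, as roughly 64-91% across the Weibull shapes tried, and 73-83% when anchored on Table 1. Only the first is comparable with 5.4. These ranges rest on assumed hazard shapes. The gap closes only in the extreme case where all failures fall on Day 7.

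The LOCF effect is smaller: 3.5 or 7 percentage points for 2 or 4 of 40 sets. It arises only if the rule is applied to sets withdrawn while functioning.

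**What to change.** Restate 7.3 before analysis as follows:

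- For each day d from 1 to 7, report the cumulative proportion of Week 2 and Week 3 insulin sets with no primary-endpoint failure (6.1.2, Primary Endpoint) from insertion through the end of day d. A failed set counts as failed on every later day.
- Estimate this by Kaplan-Meier from insertion, censoring sets withdrawn while functioning. State in 7.2 that this replaces LOCF for this endpoint; the two cannot both apply.
- State whether a failed insertion is a Day-0 failure in the primary analysis or is reported only under the secondary device-failure endpoint. Section 4.4 treats a set as failed after three unsuccessful attempts, while 6.1.3 lists inability to pierce skin as secondary.
- State likewise how a set removed for dislodgement or another mechanical fault counts. The 30% in 5.4 treats mechanical malfunction as failure, but 6.1.3 places it in a secondary endpoint.
- State that only the cumulative Day-7 value is compared with the 30% in 5.4. Daily conditional rates may be shown as a labelled supplement.

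The cost is protocol and SAP wording, plus use of recorded failure and removal times. The reported daily percentages may be lower and less favourable. Kaplan-Meier also assumes that withdrawal of a working set is unrelated to its impending failure, so the reasons for withdrawal should be listed.

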7.4 Analysis of the Secondary Endpoint(s)

Secondary analyses will use the both ITT and PP populations for analysis.

7.5 Safety Analyses

Tolerability of the extended wear Achilles cannula will be assessed by VAS scores from day of insertion through Day 7 of use. These data will be summarized using descriptive statistics.

All adverse events (AEs) will be defined and classified per study definitions. Descriptive statistics (number of participants and per-subject incidence) will be presented by level of seriousness and relationship to the study device.

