Subject will have completed all study protocol requirements at the end of the third extended wear period (*Week 3*) regardless of actual total days of Achilles infusion set wear. See Figure 1 for a Study Schema overview.

3 Study Justification

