6.1.3 Secondary Endpoints

The secondary endpoints of this study include:

- Achilles infusion set device function as evidenced by the absence of device failure with or without uncontrolled hyperglycemia. Device failure is defined as:
 - Cannula dislodgement from subcutaneous space (with or without liquid leakage at the cannula infusion site), or
 - other Achilles device malfunction (e.g., inability to pierce skin, bending, kinking or other malformation that might impact insulin infusion, securement failure).

SEE ABOVE NOTE
- Standard glucose control measures obtained from Continuous Glucose Monitoring, including observed hyper- and hypoglycemic episodes.
- Subject tolerability levels for the initial manual Achilles infusion set insertion, daily wear and final removal will be assessed using a visual analog pain scale (VAS).
- The incidence, seriousness and potential relationship infusion site to the investigation device of all adverse events will be documented and reported.

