6.1.4 Variables to Assess

The variables assessed in this study include:

- Frequency of pump prime events (i.e infusion set change out) as evaluated from the 14d pump data downloaded during the screening visit as well as during the evaluation periods

- Interstitial glucose values as measured by the CGM, downloaded at each visit to the study center
- Capillary blood glucose values measured by fingerstick measurements, downloaded from the glucose meter/recorded in Patient Diary
- Ketone values measured by fingerstick measurements, downloaded from the ketone meter/recorded in Patient Diary
- Daily pain assessments from the VAS recorded in Patient Diary
- Number of Achilles infusion set failures per definition in sections 6.1.2 and 6.1.3
- Number of hyperglycemic events (CGM, Patient Diary)
- Number of hypoglycemic events (CGM, Patient Diary)

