7.7 Tabulation of Individual participant Data

Listings of the primary and secondary endpoints will be presented by patient and by time point for each treatment.

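### Section 7.5 summarises adverse events only per subject, pooling the saline week with the insulin weeks and ignoring wear time that runs from zero to 7 days per set

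*Combined protocol and SAP*

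**What the plan says.** Section 7.5 (Safety Analyses) fixes the adverse event summary: "Descriptive statistics (number of participants and per-subject incidence) will be presented by level of seriousness and relationship to the study device". It names no other split and no other denominator.

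Glucose events are left more open. Section 6.1.3 makes the secondary endpoint "Standard glucose control measures obtained from Continuous Glucose Monitoring, including observed hyper- and hypoglycemic episodes". Section 6.1.4 lists "Number of hyperglycemic events (CGM, Patient Diary" among the variables, with a matching entry for hypoglycemia. Section 7.4 adds only "Secondary analyses will use the both ITT and PP populations for analysis", so no statistic is stated.

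Exposure varies by design:
- Under Sections 1.4.1 and 2.9, Week 1 is 7 days of saline through the Achilles set, worn alongside the participant's own insulin set. Weeks 2 and 3 are insulin wears of up to 7 days each, ended early by set failure.
- Three failed insertions on Day 0a end participation, three on Day 0b cost one insulin wear, and Week 3 may be declined.
- Section 6.2.4 gives each wear as 0-7 days, and Section 2.9 counts a participant as complete "regardless of actual total days of Achilles infusion set wear".

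Two provisions give some detail over time. Section 7.7 states "Listings of the primary and secondary endpoints will be presented by patient and by time point for each treatment", and Section 7.3 states "The primary study endpoint is the proportion of Achilles infusion sets that function each day of use, up to 7 days".

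**The concern.** Section 3.3 says the cannula has not yet delivered insulin in humans and that this study will assess safety and tolerability. Sections 4.4 and 5.5 name the primary risks of extended wear as glycemic episodes and site irritation or infection. A reader will want to know how often these occur on a set worn with insulin for up to 7 days.

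Per-subject incidence does not answer that. A participant with a reaction at every set counts once, as does one with a single reaction. A reaction in the saline week enters the same figure as one under insulin. A participant whose sets come out on the first day has had little time to develop a reaction, yet contributes a full unit to the denominator. The result cannot be read as a risk per 7-day insulin wear or set beside a per-set or per-day rate.

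Two attribution gaps add to this. In Week 1 the participant wears the Achilles set, their own set and a CGM sensor, so a site event needs a named site. After a failure in Week 2 or 3 the participant moves to a commercial set while CGM continues, and no rule says which set later events count against.

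**Working it through.** The plan gives no adverse event rate, and Section 5.3 states no hypothesis, so there is no planned figure to reproduce. The check is an illustration of size.

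**Inputs from the document.** 30% of sets performing adequately to Day 7 (comparator result, Section 5.4). Commercial failure above 15%, 25% and 65% at Days 1, 3 and 7 (Table 1, Section 4.7). Week 1 of 7 days and two insulin wears of up to 7 days (Section 1.4.1).

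**Assumptions.** The daily event rate r is constant and unrelated to failure, with r = 0.02 per wear-day and a range of 0.01 to 0.04. The failure hazard is constant. Week 1 is worn in full and both insulin sets are started.

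**Step 1, mean insulin wear.** h = -ln(0.30)/7 = 0.172 per day. Mean wear = (1 - 0.30)/0.172 = 4.07 days, or 58% of 7. Interpolating Table 1 linearly instead, with its bounds taken as exact, the area under the curve is 0.925 + 1.6 + 2.2 = 4.725 days, or 68% of 7.

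**Step 2, exposure in the pooled table.** 7 + 2 × 4.07 = 15.1 days against 21, which is 28% lower. With Table 1, 7 + 2 × 4.725 = 16.45 days, which is 22% lower.

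**Step 3, per-subject incidence.** With T = min(Exp(h), 7), E[exp(-rT)] = h/(h+r) × (1 - exp(-7(h+r))) + exp(-7(h+r)). At r = 0.02 this is 0.923.
- Two insulin wears: 1 - 0.923² = 14.8%, against 1 - exp(-14r) = 24.4% with full wear.
- With the saline week: 1 - exp(-7r) × 0.923² = 25.9%, against 1 - exp(-21r) = 34.3%.

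| r per wear-day | Insulin wears only: early failure v full wear | With saline week: early failure v full wear |
|---|---|---|
| 0.01 | 7.8% v 13.1% | 14.0% v 18.9% |
| 0.02 | 14.8% v 24.4% | 25.9% v 34.3% |
| 0.04 | 27.1% v 42.9% | 44.9% v 56.8% |

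**Step 4, events that end the wear.** If the failure is itself a hyperglycemic event, a set failing at day t has 1 + r × t expected events, against 7r for a full wear. The early failure shows fewer only if r > 1/(7 - t): above 0.20 per day for t = 2, and above 0.44 for t = 4.725. At r = 0.1 the day-2 failure shows more events (1.2 v 0.7); at r = 0.5 it shows fewer (2.0 v 3.5).

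**Step 5, does a wear-day denominator cure it?** Take an assumed 0.05 events per set-day and 40 insulin sets. Full wear gives 14.0 events in 280 days, Table 1 wear gives 9.5 in 189, and failure of every set at day 2 gives 4.0 in 80. All three return 0.05.

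**The case against.** A reader might infer that early failure always makes the set look safer. The document does not support that. Unexplained hyperglycemia, hyperglycemia with ketones, and signs of infection are failure criteria (Sections 1.4.1 and 6.1.2), so such a failure is itself an event. At the low daily rates used above, Step 4 shows the direction reverses for them. Section 7.3 also reports function on each day and makes that a preliminary safety endpoint, so early failure is in plain view.

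A reader might also infer that glucose events will be reported as raw counts. Section 6.1.4 is a list of variables, not an analysis. The CGM measures in Section 6.1.3 are not itemised and could be time-normalised. The supportable statement is that no statistic is given.

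The saline week is not ignored: Section 1.4.1 names its adverse events as outcomes, Section 6.1.2 gives it its own endpoints, and with 20 participants the Section 7.7 listings would let a reader separate the weeks by hand. Per-subject incidence is a legitimate summary, the only planned external comparison (Section 5.4) concerns set performance, and there is one arm with no hypothesis.

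All of this stands, and it narrows the point. But a listing is not a summary, and daily function says nothing about the frequency of itching, bruising, small areas of erythema or hypoglycemia, none of which is a failure criterion.

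**Conclusion.** The gap is real but limited. Section 7.5 states one adverse event summary, and nothing elsewhere adds one by saline versus insulin week, per set or per wear-day. For events that do not end the wear, early failure lowers reported incidence at the same daily rate. For hyperglycemia and infection the direction is not predictable without the background rate, which is also a reason to report exposure.

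Under the stated assumptions the pooled table rests on 28% less exposure than full wear (22% using Table 1), and incidence at 0.02 per wear-day is 25.9% v 34.3%. A shortfall of 42% (4.07 of 7 days) applies only to the insulin wears taken alone, so it overstates the effect on the table that Section 7.5 plans. All event rates are assumed. If events on the commercial set after failure are counted, follow-up is not cut short as modelled.

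This affects how the safety result can be read. It does not touch the sample size, an error rate or the success criterion.

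**What to change.** In Section 7.5, keep the per-subject table and add:
- separately for Week 1 (saline) and Weeks 2-3 (insulin), the proportion of sets with each device-related event and the rate per 100 Achilles wear-days;
- a rule assigning each event to the set in place when it began, so that events on a commercial set after failure are not counted against Achilles;
- for site events, the site affected (Achilles, the participant's own set, or CGM).

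In Section 7.4, state that hyper- and hypoglycemic episodes will be reported per Achilles wear-day.

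The cost is one derived variable, one extra table and one field on the adverse event form. Section 11 already requires dates of use and of return or explant, and Section 2.3 the date of failure. The definition of a wear-day should say which date ends the wear, since return to the site may come later than removal.

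The rates will be imprecise. At the wear in Step 1, 40 insulin sets give 40 × 4.07 = 163 wear-days and about 3.3 events at 0.02 per day. Three observed events would be 1.8 per 100 wear-days, with an exact 95% Poisson interval (0.62/163 to 8.77/163) of about 0.4 to 5.4, before any allowance for repeated sets in one participant. The table should show events and wear-days beside each rate.
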